Clinical Study Protocol

ClinicalTrials.gov entry no.	NCT05029739
Version number	1.0
Date of ethical approval	July 13, 2021

A Mobile Intervention for Patients with Peripheral Artery Disease (I-PAD): a Prospective Randomized Open Blinded End-point (PROBE) study

I. BACKGROUND AND SIGNIFICANCE

Peripheral artery disease (PAD) is a highly prevalent atherosclerotic syndrome with an estimated global population burden of ~200 million people (1). Patients with PAD are at heightened risk for adverse cardiovascular and limb events and impaired quality of life (2). Cigarette smoking is the most important modifiable risk factor for PAD. Patients with PAD who smoke have higher disease progression rates, greater risk of complications, poor post-procedural outcomes, compromised functional status, and increased hospitalizations, accounting for a higher patient and societal burden (3).

A significant goal of PAD treatment includes risk factor modification and prevention of cardiovascular events. Guideline directed therapy includes cardioprotective pharmacotherapies (i.e., antiplatelet therapy; statins; and blood pressure control, preferably with angiotensin-converting enzyme inhibitors (ACE-I) or angiotensin receptor blockers (ARBs)), and lifestyle modification (i.e., changes in diet, physical activity, and smoking cessation) (2). Nevertheless, adherence to pharmacologic and lifestyle recommendations in PAD is uncertain (4). Effective non-pharmacologic therapies for PAD also exist, including smoking cessation, exercise support, and diet counseling (5). However, limited data is available on mobile applications offering digitally delivered lifestyle change support, including a structured exercise program and smoking cessation support (6). This study aims to digitally provide lifestyle change support, including a structured and PAD-focused lifestyle program and smoking cessation support via a mobile platform (Sidekick Health) with the primary aim to increase patients' walking ability and secondary aims to reduce smoking and improve medication adherence.

II. SPECIFIC AIM

The specific aim is to determine whether a 12-week digitally delivered behavior change intervention for patients with peripheral artery disease increases walking ability, reduces smoking, improves quality of life and improves medication adherence. A follow-up visit after 12 months will be planned, to assess longer term effect on outcomes and healthcare cost.

Hypotheses

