- a) At the end of the 12 weeks, the interventional arm will reach a clinically meaningful change in walking ability, as compared to controls, measured by a change in the 6-MWT at twelve-week, and 12 months; the minimal clinically important difference (MCID) is defined as +12m (7).

- b) At the end of the 12 weeks, $\geq 15\%$ interventional treatment arm participants will give up smoking or have significantly reduced their daily smoking compared to less than $\leq 10\%$ in the control arm.
- c) At the end of the 12 weeks, $\geq 50\%$ of interventional treatment arm participants will improve their medication adherence from pre- until post-intervention as compared to $< 30\%$ in the control arm.
- d) Healthcare cost will be reduced at 12 month follow-up in the intervention arm.

III. METHODOLOGY

We will implement a randomized controlled study of a 12-week lifestyle intervention for patients with peripheral arterial disease, delivered via the digital platform Sidekick Health. Participants will be recruited and randomized in a 1:1 manner to the digitally delivered intervention + standard of care or standard of care only. The standard of care group will receive an information leaflet on important lifestyle factors for PAD and smoking cessation and medical adherence will be encouraged by the health care provider. The interventional arm will receive a digital program delivered to their mobile phone alongside standard of care. Replicating a real-life scenario a personalized approach will be applied in the interventional arm, especially regarding smokers. Therefore, two pathways are possible in the interventional arm in this trial, one for smokers who want assistance in smoking cessation (PAD-SC) and another for non-smokers or those who smoke and do not desire to quit (PAD-Reg). Patients will be followed up at 12 weeks. We aim to do a separate follow-up at twelve months. The primary outcome will be a change in pain-free and maximal walking ability, measured by the 6-minute walking test. Secondary outcomes will include smoking status change (in PAD-SC group as compared to the control arm), medication adherence and lifestyle changes (increased physical activity, changes in self-assessed stress/energy/sleep quality levels), health-related quality of life, and a reduced need for hospitalization or revascularization due to PAD at 12 months of follow up.

Subject selection

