After recruitment, measurements and data collections will occur at each clinic by a experienced clinic or research nurse, as shown in table 2 and further detailed under section VIII. Furthermore, a 6-minute walking test will be administered by a trained clinic nurse at baseline, after 12 weeks and for a separate follow-up at 12 months. The American Thoracic Society protocol for the 6-minute walking test, modified for patients with intermittent claudication (IC), will be used. The 6MWT has excellent test-retest reliability for patients with IC. (8, 9). A central computerized procedure will randomly assign participants to treatment arms, stratified for study site and smoking status.

Intervention:

Participants will be instructed to download the SKH mobile app, and they will receive an access code to activate the PAD lifestyle change program. After the first week of the program, participants who smoke will be offered to incorporate smoking cessation support into their PAD program. These changes are minor and not intended to divide the intervention group in two but instead personalize the experience. Personalization of the program is essential for engagement and to deliver the most meaningful impact on clinical outcomes. The program aims to empower positive lifestyle change by gamification, altruistic rewards, and engaging content with relevant tasks or missions to be completed. Beyond this, all patients in the interventional arm will also receive standard of care as defined below for the control arm.

Participants in the intervention group will also be asked to do a separate and virtually delivered 6-minute walking test to validate the digital in-app 6MWT.

Control:

All patients in the control arm will receive best medical treatment including start or optimization of secondary preventive pharmacotherapy, smoking cessation advise and advise on modifiable risk factors. The control arm will also receive an information leaflet about relevant lifestyle modifications for PAD. After baseline measurements and data collection, there will be no scheduled visits by a health care provider until week 12.

Table 2. Timing of Proposed Data Collection and Instruments Used

Data collection/Instruments	Baseline	Post-Intervention (after week 12)	12-month follow-up
All participants (intervention and control)			
Demographic and Clinical/Medical Baseline Information (e.g., tobacco use, other risk factors, and comorbidities)	Yes	Yes	Yes
6-Minute Walking Test	Yes	Yes	Yes

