Vascular Quality of Life Questionnaire (VascuQoL-6)	Yes	Yes	Yes
Morisky Medication Adherence Scale (MMAS-8)	Yes	Yes	Yes
Quality of life questionnaire – assessed by EQ5D5L	Yes	Yes	Yes
Assessment of health literacy (HLS-EU-Q16 Swedish version)	Yes	-	-
Carbon Monoxide breath monitor (smokers only)	Yes	Yes	Yes
Smoking Readiness to Quit Ladder (smokers only)	Yes	Yes	Yes
Daily frequency of cigarettes smoked (smokers only)	Yes	Yes	Yes
Intervention arm only			
In-app 6-minute walking test	Yes	Yes	Yes
Free-living physical activity (measured as total step count per day)	Yes (week 1)	Yes	-
In-app metrics (e.g. stress/sleep/energy level self-assessment)	Yes (week 1)	Yes	-

Measures – copies of questionnaires will be included in this protocol when finalized in section VIII below (Study Questionnaires)

IV. BIOSTATISTICAL ANALYSIS

Variables to be collected

Participants' demographic and background information, including age, gender, height, weight (and BMI), tobacco use, co-morbid medical or psychiatric conditions, and information on any current medical therapy they may or may not be receiving will be collected. All participants should be on the best medical PAD treatment available for them, and the control arm will receive an information leaflet about relevant lifestyle modifications for PAD. A 6MWT, questionnaires, and validated survey instruments (10) will be administered both pre-and post-intervention and 12 months from the start of the intervention.

Primary Outcomes (Intervention KPIs)

As far as possible, evaluation of endpoints will be done by evaluators blinded to the treatment assignment (PROBE design).

- Walking Ability: Change in patients objectively measured walking ability (measured by the 6-Minute Walk Distance Test) from pre- to post-intervention and 12 months.

Secondary Outcomes

- Smoking status: Change in patients' daily smoking patterns from pre to post-intervention and at twelve months. This will be based on information from the patient, supported by read-outs from the carbon monoxide breath monitor at baseline, 12 weeks and one year.
- Medication adherence improvement.
- Lifestyle behavioral changes (measured in-app):
 - Changes in free living physical activity, measured as total step count per day (from baseline to week 12)
 - Changes in self assessed stress levels, measured on an ordinal scale from 0-10 (from baseline to week 12)
 - Changes in self assessed energy levels, measured on an ordinal scale from 0-10 (from baseline to week 12)

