 - Changes in self assessed sleep quality, measured on an ordinal scale from 0-10 (from baseline to week 12)

- Disease-specific health-related quality of life.
- Increased readiness to quit smoking.
- Comparing outcomes to health literacy.
- Comparing healthcare costs between groups. Following completion of the long-term follow-up at 12 months for all patients, a separate cost-effectiveness analysis will be undertaken, based on the prospectively collected EQ5D-5L data and accumulated costs per patient as registered in the participating hospital's cost-per-patient databases. Quality Adjusted Life Years (QALYs) and Incremental Cost-Effectiveness Ratio (ICER) will be the main analyzed endpoints.

[figure not shown]
Retention and Engagement

- Program uptake (number of app downloads, how many participants/potential quitters registered (including gender and age)
- Length of program participation
- Program usage patterns (how often do people visit, how many tasks are performed, which tasks (videos, daily tasks, other) are used/accessed, etc.)
- Pre/post assessment of medication therapy (as registered medication taken)

End of study

The formal trial completion is when the recruited patients have completed the 12-week intervention, but an extended follow-up at twelve months from study start will also be arranged.

IPAD STUDY DESIGN

Statistical Methods

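### The primary outcome is worded two ways (pain-free and maximal walking ability; one 6-minute walk distance to two time points), and no rule says which result decides the trial

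*Combined protocol and SAP*

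**What the plan says.** The protocol describes the primary outcome in three places.

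- Section III, Methodology: "The primary outcome will be a change in pain-free and maximal walking ability, measured by the 6-minute walking test". This names two aspects of walking, and the sentence itself gives no time point.
- Section IV, Primary Outcomes: "Change in patients objectively measured walking ability (measured by the 6-Minute Walk Distance Test) from pre- to post-intervention and 12 months". This is one distance with two follow-up times, and pain-free walking does not appear.
- Section II, hypothesis (a): it opens with "At the end of the 12 weeks, the interventional arm will reach a clinically meaningful change in walking ability" but goes on to say the change is "measured by a change in the 6-MWT at twelve-week, and 12 months".

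Other passages bear on the time point. The Specific Aim says "A follow-up visit after 12 months will be planned, to assess longer term effect on outcomes and healthcare cost". Methodology says "We aim to do a separate follow-up at twelve months". Study procedures schedules the walking test "at baseline, after 12 weeks and for a separate follow-up at 12 months". End of study says "The formal trial completion is when the recruited patients have completed the 12-week intervention, but an extended follow-up at twelve months" will also be arranged.

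Statistical Methods sets one two-sided 5% significance level for the whole plan. It allows either ANCOVA or mixed (repeated-measures) ANOVA for the primary outcome and adjusts for covariates that differ significantly between the groups. It ranks no results, splits no alpha, and does not say whether one or several results must be positive.

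Section VIII refers to an Appendix A for the walking-test protocol. That appendix is not in the text supplied for review.

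**The concern.** A primary outcome has to say in advance which result makes the trial positive. Here two readers could apply the same plan to the same data and disagree. Suppose pain-free distance improves significantly and total distance does not. The Methodology wording could support a claim of success; the Primary Outcomes wording could not. Or suppose distance differs at 12 months but not at week 12: the outcome list includes that result, while much of the surrounding text treats it as later follow-up.

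The choice could then be made after the results are known. If that amounts to accepting whichever of two results is significant, the 5% error level no longer holds.

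**Working it through.** **1. The two definitions side by side**

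| Item | Methodology (III) | Primary Outcomes (IV) |
|---|---|---|
| Measure | pain-free and maximal walking ability | 6-minute walk distance |
| Time point | none in the sentence | post-intervention and 12 months |
| Pain-free walking | included | absent |

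Maximal ability may be the same quantity as the 6-minute distance, but the supplied text does not say so. Even if it is, pain-free walking is primary in one place and missing in the other.

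**2. The plan's own sample size**

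Inputs from Subject enrollment: f = 0.15, α = 0.05, power 0.80, r = 0.25 between baseline and final time point, two groups. For a group-by-time interaction with m = 2 measurements:

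λ = f² × N × m / (1 − r) = 0.0225 × 134 × 2 / 0.75 = 8.04, with 1 and 132 degrees of freedom.

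Power is 80.4% at N = 134 and 79.8% at N = 132, so the stated 134 reproduces. It rests on one effect size and two measurements. It does not cover a second primary measure, and it does not show which visit is the final time point.

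**3. Error if either of two results suffices (each tested at two-sided 0.05)**

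Independent results: 1 − 0.95² = 9.75%. In the direction of benefit only: 1 − 0.975² = 4.94%. For correlated results, the risk is 1 minus the bivariate normal probability that both |Z| ≤ 1.96; for benefit only, 1 minus the probability that both Z ≤ 1.96.

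| Assumed correlation of the two test statistics | Any false positive (nominal 5%) | False claim of benefit (nominal 2.5%) |
|---|---|---|
| 0 (theoretical ceiling) | 9.75% | 4.9% |
| 0.5 | 9.1% | 4.5% |
| 0.8 | 7.8% | 3.9% |
| 0.9 | 7.0% | 3.5% |

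The documents give no correlation between the two results, so these values are assumptions. The stated r = 0.25 is a different quantity (baseline with final visit). The value 0.5 is what two change scores sharing a baseline would have if variances and between-visit correlations were all equal: (1 − r) / [2(1 − r)] = 0.5.

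**4. Readings with no inflation**

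Requiring both results, or using one group-by-time test on one distance, keeps the error at or below 5%. Requiring both costs power. With the test behind N = 134 (80.4% each), joint power is 65%, 69% and 73% at correlations 0, 0.5 and 0.8, provided the planned effect applies to both results.

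**5. Power of one baseline-adjusted ANCOVA at the same inputs**

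In this design f = 0.15 corresponds to a between-group difference of 4f = 0.6 SD. Residual variance after baseline adjustment is 1 − 0.25² = 0.9375.

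λ = 0.6² × 134 / 4 / 0.9375 = 12.86, giving 94.5% power.

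Requiring two such results gives 89%, 90% and 92% at correlations 0, 0.5 and 0.8, again only if the planned effect holds for both. If one effect were 75% of plan (an assumption), its λ would be 0.75² × 12.86 = 7.24 and its own power about 76%, which caps joint power below 80%.

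**The case against.** The strongest reply is that the time point is largely settled. Hypothesis (a) opens at the end of 12 weeks; the Specific Aim, Methodology and Study procedures treat 12 months as longer-term or separate; and formal completion is tied to the 12-week intervention. That stands, and it makes the timing issue mainly one of wording. It does not close it, because Primary Outcomes and hypothesis (a) both still include 12 months and no passage says week 12 alone decides. Nor does it settle pain-free against maximal walking.

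Second, Appendix A may define the measures. It may, and confidence on that part is limited accordingly. A walking-test procedure would be an unlikely place for a decision rule.

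Third, a reader might infer that the plan runs a false-positive risk of nearly 10%. The documents do not support that. No passage says that either result is enough; the conjunction in the Methodology sentence is equally open to a both-required reading, and a single mixed-ANOVA test on one distance would not inflate the error at all. The 9.75% figure also needs zero correlation, which is implausible for two readings from the same test in the same patients.

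**Conclusion.** The inconsistency is real and should be resolved, because it governs what counts as a positive trial. The substantial gap is pain-free against maximal distance. The status of the 12-month result is a smaller gap, since week 12 is the better supported time.

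The size is conditional. Under an either-suffices rule, which the plan does not state, the false-positive risk is about 7.0% to 9.1% against 5%, and false claims of benefit 3.5% to 4.5% against 2.5%, for assumed correlations of 0.9 to 0.5. The finding is therefore that the plan leaves room for such inflation, not that it commits to it. Appendix A could clarify the measures and should be checked.

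**What to change.** Before any between-group data are seen, align four places on one primary measure, one time point and one test: hypothesis (a), the outcome sentence in Methodology, the Primary Outcomes entry, and Statistical Methods.

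The option best supported by the text is the between-group difference in 6-minute walk distance at week 12, by intention to treat, using ANCOVA with baseline distance as a prespecified covariate, tested once at two-sided 0.05. Any further covariates should be fixed in advance, including a decision on the stratification factors (site and smoking status). This replaces the rule of adjusting for variables that differ significantly at baseline; while that rule stands, the deciding test is not fully specified.

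Pain-free distance and the 12-month results become secondary, or are tested in a stated fixed order, each at 0.05 only if every earlier test is significant. The sponsor may choose a different measure or order, provided it is written down. A both-required rule is not recommended as it stands: its 89% to 92% power assumes the planned effect on both results, and the documents give no input for the second.

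The cost is wording. Alpha stays at 0.05 and N at 134. The downside is that a result outside the named test, such as a benefit seen only in pain-free distance or only at 12 months, can no longer make the trial positive on its own.

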Individuals willing to participate and who provide written informed consent to the study will be further assessed and screened based on the inclusion and exclusion criteria presented in Table 1.

Table 1. Participant Criteria

Inclusion	Exclusion
Adults with confirmed PAD referred to a vascular surgery unit for evaluation and treatment, currently on best medical treatment and own/have access to a mobile smartphone	Critical limb ischemia, prior amputation, or other diseases/impairment that limit the walking ability and the 6-minute walk test's proper conduct
Stable PAD disease and limb symptoms during the last 3 months.	Cognitive impairment
PAD is the activity-limiting disease	Prior revascularization less than one year ago
Abnormal resting ankle-brachial index (≤ 0.90), falsely elevated above 1.3 or a 30% post-exercise ABI reduction.	A planned revascularization procedure during the upcoming 12 months (known at baseline)

Subject enrollment

Patients will be recruited by a clinic nurse or a medical doctor at participating centers (via telephone or during a scheduled in-person visit). Once agreed to participate and after signing informed consent, then the inclusion and exclusion criteria will be explored. Patients failing the screening process (do not meet the inclusion/exclusion criteria) may not participate in this study. Reasons for screen failure will be documented, but no other data will be collected. Participants who meet the criteria will be randomized to intervention or usual care in a 1:1 manner.

Based on a G*power analysis, the total number of patients in the two groups (intervention and control) will be 134, 67 in the intervention group and 67 in the control group, with an anticipated effect size of $f = 0.15$, $\alpha = 0.05$, power = 0.80 and correlations between time points (baseline and final timepoint) estimated at $r=0.25$. Foreseeing an attrition rate of 15%, we aim to recruit 155 patients to the trial.

Study procedures

All participants:

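### The smoking outcome is set as PAD-SC pathway versus control arm: a self-selected subgroup against a randomised arm, at odds with hypothesis (b) and intention-to-treat

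*Combined protocol and SAP*

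**What the plan says.** The places that bear on the smoking comparison are these.

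- **III. Methodology, overview.** "Secondary outcomes will include smoking status change (in PAD-SC group as compared to the control arm". This is the only place that names the groups to be compared for the smoking outcome as an outcome.
- **III. Methodology, pathway definitions.** The intervention arm has two pathways: "one for smokers who want assistance in smoking cessation (PAD-SC) and another for non-smokers or those who smoke and do not desire to quit".
- **III. Methodology, Intervention.** The split comes after allocation: "After the first week of the program, participants who smoke will be offered to incorporate smoking cessation support into their PAD program". The changes are said to be "not intended to divide the intervention group in two but instead personalize the experience".
- **III. Methodology, Study procedures.** "A central computerized procedure will randomly assign participants to treatment arms, stratified for study site and smoking status". Desire to quit is not a stratification factor.
- **II. Specific Aim, hypothesis (b).** At least 15% of the intervention arm, against at most 10% of the control arm, is the target: "interventional treatment arm participants will give up smoking or have significantly reduced their daily smoking". It carries no PAD-SC restriction and no smoker denominator.
- **IV. Biostatistical Analysis, Secondary Outcomes.** The smoking outcome is change in "daily smoking patterns from pre to post-intervention and at twelve months", for patients generally.
- **IV. Biostatistical Analysis, Statistical Methods.** Both intention-to-treat and per-protocol analyses are planned. The PAD-SC comparison is not assigned to either.
- **Table 2.** Cigarettes per day, breath carbon monoxide and the readiness-to-quit ladder are collected from smokers in both arms at all three time points.

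**The concern.** Membership of PAD-SC depends on a choice made about a week into the programme, and only intervention patients are offered it. The control arm has the same mixture of willing and unwilling smokers, but no offer reveals who is who and no matching control subset is defined. The comparison therefore sets motivated smokers against a mixture. Randomisation balances smokers between arms; it does not balance PAD-SC against control.

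Two things are at stake. First, self-selection can be reported as an effect of the app on smoking, which is a named aim of the trial. Second, the plan holds two incompatible populations for one outcome and does not say which will be reported, so the choice could be made after the results are seen.

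**Working it through.** **The plan's own figures.** There is no sample size or power for smoking. The overall size does reproduce for the primary outcome: with f = 0.15, r = 0.25 and two time points, λ = f²·N·m/(1−r) = 0.0225 × 134 × 2 / 0.75 = 8.04, giving power 0.804 at N = 134. That figure is not disputed and is used only to scale the number of smokers.

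**Bias under zero effect.** Let p be uptake of PAD-SC among intervention smokers, and q_w, q_u and q_c the success rates of willing, unwilling and all control smokers. With no app effect:

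- q_c = p·q_w + (1−p)·q_u
- so q_w = [q_c − (1−p)·q_u]/p
- and the spurious difference is q_w − q_c = (1−p)·(q_w − q_u)

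This is positive whenever p < 1 and q_w > q_u. Example: q_c = 0.10, p = 0.5, q_u = 0.05 gives q_w = (0.10 − 0.025)/0.5 = 0.15.

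**Inputs, all assumed.** q_c = 10% (hypothesis (b) gives 10% for the control arm, not for its smokers); q_u from 5% down to 0%; p from 30% to 80%; 40% smokers, giving 31 per arm (0.40 × 155/2) or 26 (just under 0.40 × 67 = 26.8). The comparator is control smokers. Rejection is for Fisher's exact test, two-sided p < 0.05, by full enumeration with the number of PAD-SC takers binomial(n, p).

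| Uptake | PAD-SC rate, no effect | Rejection, 31 per arm | Rejection, 26 per arm |
|---|---|---|---|
| 30% | 21.7–33.3% | 12.8–33.7% | 10.0–26.7% |
| 40% | 17.5–25.0% | 8.1–20.3% | 6.6–16.3% |
| 50% | 15.0–20.0% | 5.6–12.3% | 4.8–10.3% |
| 60% | 13.3–16.7% | 4.1–7.7% | 3.6–6.6% |
| 70% | 12.1–14.3% | 3.1–4.8% | 2.6–4.1% |
| 80% | 11.3–12.5% | 2.7–3.5% | 2.3–3.0% |

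All smokers compared by arm: 10% against 10%, rejection 1.0% at either size.

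**Milder selection.** Fix q_w/q_u at 1.5 to 3 and p at 30–70%, keeping q_c = 10%. PAD-SC shows 11.1–18.8%, a spurious gain of 1.1 to 8.8 points. Rejection is 2.5–9.0% (31 per arm) and 2.1–7.1% (26 per arm).

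**Other control rates.** At 50% uptake, 31 per arm, q_u from half of q_c down to 0: rejection is 2.8–5.9% at q_c = 5%, 7.5–18.4% at 15% and 11.5–34.3% at 25%. The last is what 10% of the whole arm means if 40% smoke (0.10/0.40). By arm the values are 0.2%, 1.8% and 2.6%.

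**Cigarettes per day.** Assume SD 5 and a willing/unwilling gap in change of 2–4 cigarettes. The spurious difference is (1−p) × gap, from 0.2 × 2 = 0.4 to 0.7 × 4 = 2.8 cigarettes. Simulated false-positive rates (t-test, 40,000 trials per cell) run from about 6% to 27% with 31 per arm and 6% to 23% with 26, against about 5% by arm.

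**Precision of the randomised comparison.** For 15% versus 10%, SE = √[(0.15×0.85 + 0.10×0.90)/n] = √(0.2175/n). The 95% half-width is 1.96·SE: 20.4 points at n = 20, 16.4 at 31, 14.6 at 39 (30% of 67 to 50% of 155/2). Power is about 8–10% by normal approximation and 2.4–5.2% by Fisher.

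**The case against.** The strongest reply is that the fault sits in one parenthesis of an overview paragraph. Hypothesis (b) is arm-wide, the outcome list carries no PAD-SC limit, the pathways are said not to split the arm, intention-to-treat is stated, and the sample-size text knows only two groups ("the total number of patients in the two groups (intervention and control) will be 134"). On that reading this is an inconsistency to tidy, not a settled flawed analysis. That is fair as far as it goes, and the conclusion here is confined to the comparison run as worded. But no other text overrides the parenthesis. The remark about not dividing the arm concerns app content. The per-protocol clause does not cover it either: the comparison is not labelled per-protocol, and declining an optional module is nowhere called a deviation.

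The second reply is about size. No input on uptake or success among smokers comes from the documents, and the largest rejection rates need unwilling smokers to succeed at 0%, although the outcome counts reduction as well as quitting. Even 5% implies that willing smokers succeed 4.3 times as often at 30% uptake (21.7/5). With ratios of 1.5 to 3, rejection exceeds 5% in only 4 of 15 scenarios at 31 per arm and 2 of 15 at 26. This stands: an inflated false-positive rate is possible, not certain. The bias in the estimate remains in every one of those scenarios.

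The figures also use control smokers, where the text says the control arm. Counting non-smokers in the control denominator would widen the gap further.

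Finally, this is one unpowered secondary outcome. That limits the weight of the point, but low power does not excuse a biased comparison.

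**Conclusion.** The point holds and should be fixed. As worded, the PAD-SC comparison is not randomised, has a different population from hypothesis (b), and drops randomised intervention smokers contrary to intention-to-treat. The structural conclusion needs no assumption; that the bias favours the app rests only on incomplete uptake and on willing smokers doing better than unwilling ones.

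Its size does depend on assumptions. With 10% success among control smokers, the spurious gain is 1.1 to 8.8 points under moderate selection and larger if unwilling smokers rarely succeed. At 70–80% uptake in that case, the responder estimate is still biased but Fisher rejection stays below 5%. Allocation, the primary walking outcome and hypothesis (b) read for the whole arm are not affected.

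**What to change.** 1. In III. Methodology, replace the parenthesis with: *in all participants who smoke at baseline, compared between randomised arms regardless of PAD-SC uptake*.
2. State the same population for the smoking outcome in section IV, and make baseline smokers the denominator in both arms of hypothesis (b).
3. Report PAD-SC uptake and results descriptively. If PAD-SC is compared with control smokers of similar baseline readiness (the ladder is collected in both arms), label that supportive and non-randomised.
4. Adjust for site where the model is stable, for example for cigarettes per day; do not require it for the sparse responder outcome.
5. Say that the responder comparison has low power, and read it through the 95% confidence interval that Statistical Methods already promises for between-group differences.

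Items 1 and 2 are the essential change; items 3 to 5 support it. The cost is wording: smoking status is already a stratification factor and the smoking data are already collected in both arms. There are two downsides. The estimated effect will probably be smaller, because smokers who decline PAD-SC are included. The interval will also be wide, about ±15 to ±20 points. The change removes the selection bias; it does not make the responder comparison informative.
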